#### STUDY SESSION 1 (PK study)

**Procedure Day 1:** Four Flector® patches [140 cm^2 each; two patches/arm] will be applied for 10 h and removed. Blood samples will be collected at specified times.

**Procedure Day 2:** Blood samples will be collected at specified times.

**Procedure Day 3:** Blood samples will be collected at specified times. There will be at least a one week washout period before proceeding to the next study session.

#### STUDY SESSION 2 (PK study)

**Procedure Day 4:** Pennsaid® topical solution [4 g of solution over 400 cm^2 area; 2 g/200 cm^2 on each upper arm] will be applied to the skin for 6 h and removed. Blood samples will be collected at specified times.

**Procedure Day 5:** Blood samples will be collected at specified times.

**Procedure Day 6:** Blood samples will be collected at specified times. There will be at least a one week washout period before proceeding to the next study session.

#### STUDY SESSION 3 (TS study)

**Procedure Day 7:** Six sites (3 sites/arm/product) will be designated on the volar forearms for each diclofenac product and 1 site for a negative control (volar skin area where no drug is applied). Flector® 1.3% patches [8.25 cm^2 each] and Pennsaid® 2% topical solution [82.5 mg/8.25 cm^2 each] will be applied. At 10 h post application for patches and 6 h post application for solution, all products will be removed from their respective sites. Two sites for each product will be tape stripped at the designated uptake (absorption) time (10 h and 6 h post application).

**Procedure Day 8:** An additional two sites for each product will be tape stripped at the designated clearance period (27 and 23 h post application; 17 h after product removal).

**Procedure Day 9:** The remaining two sites for each product will be tape stripped at the designated clearance period (51 and 47 h post application; 41 h after product removal).

## 5 STUDY ENROLLMENT AND WITHDRAWAL

Only healthy adult volunteers who meet the inclusion/exclusion criteria will be eligible for enrollment into this study. Twelve subjects will be recruited as well as at least another five alternates who could replace subjects who drop out from the study for any unforeseen reason. The study population selected for this study includes healthy adult men and women without other comorbidities ages 18-45, inclusive. The selection criteria are designed to exclude people who might have medical conditions that could pose a safety risk and people whose medical conditions might interfere with the objectives and results of the study.

Subjects will be recruited by local advertisements to the study center, online recruitment, newspaper ads or The Elm Weekly. Potential subjects who are interested in the study will be informed of the study and if they wish to participate, will receive additional study information, including an onsite screening appointment and informed consent form. Each of the 12 selected subjects enrolled will be expected to complete all three study sessions.

We aim to target at least 40% participants of each gender. There are no specific ethnicity/race category recruitment targets, although such information will be recorded by the researchers.

## 5.1 Subject Inclusion Criteria

Subjects are eligible for this study if they fulfill the inclusion criteria specified below:

- 1. Men or non-pregnant, women who are of any ethnic background between the age of 18 and 45 years old.
- Subjects must be non-smokers (must have refrained from the use of nicotinecontaining substances, including tobacco products (e.g., cigarettes, cigars, chewing tobacco, snuff, gum, patches or electronic cigarettes) over the previous 2 months and are not currently using tobacco products.
- 3. Provide written informed consent before initiation of any of the study procedures.
- 4. Agree not to participate in another clinical trial/study during the study period or to participate in an investigational drug study for at least 1 month after the last study session.
- 5. Able to adhere to the study protocol schedule and study restrictions.
- 6. Able to participate in all study sessions.

- 7. Has a volar forearm of either at least 24 cm (9.45 inches) in length or of sufficient size that can accommodate the products to be tested in a study area that begins at least 5 cm (1.97 inches) above the wrist and ends a minimum of 0.5 cm (0.197 inches) below the antecubital fossa (i.e., the bend in the arm at the elbow).
- 8. Subjects have upper arms large enough to allow for the placement of two 140 cm^2 [21.7 in] patches (distance from acromion process of the scapula to olecranon process should be a minimum of 35 cm [13.8 inches]; circumference of upper arms should be a minimum of 28 cm [11.02 inches] and 200 cm^2 [31 in] area for application of solution.
- 9. Subjects deemed to be healthy as judged by the Medically Accountable Investigator (MAI) and determined by medical history, physical examination and medication history.
- 10. Negative urine drug screening test (cannabinoids, amphetamines, barbiturates, benzodiazepine, cocaine, methadone, opiates, PCP).
- Have normal screening laboratories for white blood cells (WBC), hemoglobin (Hgb), platelets, sodium, potassium, chloride, bicarbonate, blood urea nitrogent (BUN), creatinine, alanine transaminase (ALT) and aspartate aminotransferase (AST).
- 12. Have normal screening laboratories for urine protein and urine glucose.
- 13. Female subjects must be of non-childbearing potential (as defined as surgically sterile [i.e. history of hysterectomy or tubal ligation] or postmenopausal for more than 1 year), or if of childbearing potential must be non-pregnant at the time of enrollment and on the morning of each study day, and must agree to use hormonal or barrier birth control such as implants, injectables, combined oral contraceptives, some intrauterine devices (IUDs), sexual abstinence, or a vasectomized partner.
- 14. Agrees not to donate blood to a blood bank throughout participation in the study and at least 3 months after the last study session.
- 15. Have a normal ECG; must not have the following to be acceptable: pathologic Q wave abnormalities, significant ST–T wave changes, left ventricular hypertrophy, right bundle branch block, left bundle branch block. (sinus rhythm is between 55–100 beats per minute).
- 16. Have normal vital signs (see Appendix C)
  - Temperature 35-37.9°C (95-100.3°F)
  - Systolic blood pressure 90-165 mmHg
  - Diastolic blood pressure 60-100 mmHg
  - Heart rate 55-100 beats per minute
  - Respiration rate 12-20 breaths per minute

### 5.2 Subject Exclusion Criteria

Subjects will be excluded for any of the following conditions/reasons:

- 1. Women who are pregnant, lactating, breast feeding or have a positive serum pregnancy test at enrollment or positive urine pregnancy test on the morning of the first day of each study session.
- 2. Smokers (current use or use over the previous 2 months of nicotine-containing substances, including tobacco products (e.g., cigarettes, cigars, chewing tobacco, snuff, gum, patch or electronic cigarettes).
- 3. Participation in any ongoing investigational drug trial/study or clinical drug trial/study.
- 4. History as either reported by the subject or evident to the Medically Accountable Investigator (MAI) of infectious disease or skin infection or of chronic skin disease (e.g., psoriasis, atopic dermatitis).
- 5. History of diabetes.
- 6. History of significant skin cancers (e.g., melanoma, squamous cell carcinoma), except basal cell carcinomas that were superficial and did not involve the investigative sites.
- 7. Body Mass Index (BMI) ≥30 kg/m^2.
- 8. History of chronic obstructive pulmonary disease or cor pulmonale, or substantially decreased respiratory reserve, hypoxia, hypercapnia or pre-existing respiratory depression.
- 9. Active positive Hepatitis B, C and/or HIV serologies (see Appendix B).
- 10. Positive urine drug screening test.
- Use of any prescription medication during the period 0 to 30 days or over-thecounter medication e.g. antihistamines, topical corticosteroids during the period 0-5 days before entry to the study (vitamins, herbal supplements and birth control medications not included).
- 12. Currently taking daily oral nonsteroidal anti-inflammatory drug [NSAIDs] (aspirin, ibuprofen, naproxen, etc...).
- 13. Currently taking daily anticoagulants or within the past month prior to entry into the study (warfarin, heparin, rivaroxaban, dabigatran, etc...) ACE-inhibitors, cyclosporine, diuretics, lithium or methotrexate.
- 14. Donation or loss of greater than one pint of blood within 60 days of entry to the study.

- 15. Any prior adverse reaction or hypersensitivity to diclofenac, aspirin, ibuprofen, naproxen or other nonsteroidal anti-inflammatory drug (NSAID), other inactive ingredients in the patch or topical solution or to adhesives or tapes used to cover or tape strip the treatment sites.
- 16. Received an experimental agent (vaccine, drug, biologic, device, blood product or medication) within 1 month before enrollment in this study or expects to receive an experimental agent during the study.
- 17. Eat or drink anything containing alcohol within 24 hours prior to dose administration.
- 18. Any condition that would, in the opinion of the Medically Accountable Investigator (MAI), place the subject at an unacceptable risk of injury or render the subject unable to meet the requirements of the protocol.
- 19. Subject has an obvious difference in skin color between arms or the presence of a skin condition, excessive hair at the application site (upper arms/volar forearms), sunburn, raised moles and scars, open sores at application site (upper arms/volar forearms), scar tissue, tattoo, or coloration that would interfere with placement of diclofenac products, skin assessment, or reactions to diclofenac.
- 20. History of asthma or urticaria, hypertension, myocardial infarction, thrombotic events, stroke, congestive heart failure, impaired renal function or liver disease.
- 21. History of gastrointestinal bleeding or peptic ulcer disease.

# 6 STUDY PRODUCT

## 6.1 Study Product Description

#### 6.1.1 Flector® (diclofenac epolamine 1.3%) patch [140 cm^2]

Flector® is a prescription diclofenac-containing patch that releases diclofenac through the skin into the body. The patch releases diclofenac over a 12 h period, the recommended duration of patch application. The patch is for the topical treatment of acute pain due to minor strains, sprains and contusions.

#### 6.1.2 Pennsaid® (diclofenac sodium 2%) topical solution

Pennsaid® 2% topical solution is a prescription diclofenac-containing solution that releases diclofenac through the skin into the body. The solution releases diclofenac over a 12 h period. The solution is a nonsteroidal anti-inflammatory drug (NSAID) indicated for the treatment of the pain from osteoarthritis of the knee(s).

## 6.2 Formulation, Packaging, and Labeling

[figure not shown]
#### 6.2.1 Flector® (1.3% diclofenac epolamine) patch

Active ingredient (in each patch): diclofenac epolamine, 180 mg (13 mg per gram adhesive) in an aqueous base. In addition to the active ingredient (diclofenac epolamine), the following inactive ingredients are present in the patch: dihydroxyaluminum aminoacetate, disodium edetate, D-sorbitol, fragrance (Dalin PH), gelatin, kaolin, methylparaben, polysorbate 80, povidone, propylene glycol, propylparaben, sodium carboxymethylcellulose, sodium polyacrylate, tartaric acid, titanium dioxide and purified water. This patch is manufactured by Teikoku Seiyaku Co., Ltd. This product should be stored at room temperature.

#### 6.2.2 Pennsaid® 2% diclofenac sodium topical solution

In each pump of solution there is 1 g of solution (20 mg diclofenac sodium per gram solution). In addition to the active ingredient (diclofenac sodium), the following inactive ingredients are present in the solution: dimethyl sulfoxide USP (DMSO, 45.5% w/w), ethanol, purified water, propylene glycol and hydroxypropyl cellulose. This solution is manufactured by Horizon Pharma USA Inc. This product should be stored at room temperature.

# 7 PHARMACOKINETICS AND STATISTICAL CONSIDERATIONS

## 7.1 Study Hypothesis

#### TS and PK

The tested diclofenac products are non-bioequivalent hence, we will test the null hypothesis ( $H_0$ ) that the mean clearance/uptake diclofenac amount ratio, and the PK parameters ( $C_{max}$  and AUC) between these products are different (i.e., outside the 80–125% range).

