#### Flector® patch and Pennsaid® topical solution

# **3 OBJECTIVES**

#### 3.1 Study Objectives

1) Generate human PK data for the purpose of establishing an IVIVC model by collecting data following the application of two diclofenac formulations: Flector® 1.3% diclofenac epolamine patches and Pennsaid® 2% diclofenac sodium topical solution.

2) Generate TS data for the purpose of establishing a fundamental IVIVC model by collecting skin concentration data following the application of two diclofenac formulations: Flector® 1.3% diclofenac epolamine patches and Pennsaid® 2% diclofenac sodium topical solution.

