## 4 STUDY DESIGN

This is designed as an open-label, non-placebo controlled, crossover study. The products tested are already FDA approved; however, the products are used outside of the approved indications by using healthy subjects. The products being tested are for research purposes only; this is not a treatment study. The study is not blinded because PK and TS assessment is not subject to participant and/or observer bias. The study will consist of three study sessions. Each of the 12 selected subjects will be enrolled to complete three study sessions, nine procedure days. There will be no overnight stays during the study. There will be at least a one week washout period between each study session.

The studies are as follows:

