## 7.2 Analyses

Diclofenac concentrations will be measured in serum samples collected from each subject. Blood samples (approximately 5 mL (1 tsp)) will be collected during Study Session 1 prior to dosing and then at 1 h, 2 h, 3 h, 4 h, 5 h, 6 h, 7 h, 8 h, 9 h, 10 h, 24 h, 27 h, 30 h, 32 h and 51 h post-patch application. Blood samples (approximately 5 mL (1 tsp)) will be collected during Study Session 2 prior to dosing and then at 1 h, 2 h, 3 h, 4 h, 5 h, 6 h, 7 h, 23 h, 26 h, 29 h, 31 h and 47 h post-solution application. After the PK study, TS study will be conducted at 10 h [patches] and 6 h [solution] (skin drug uptake/absorption), 27 h [patches] and 23 h [solution] (skin drug clearance), and 51 h [patches] and 47 h [solution] (skin drug clearance) post product application. Non compartmental analyses (NCA) will be conducted to estimate the PK parameters such as: maximum serum concentration  $(C_{max})$ ; apparent elimination rate constant (k); apparent half-life (t1/2), calculated as 0.693/k; AUC0-last of the serum concentration-time determined by the linear trapezoidal method; and AUC value extrapolated to infinity (AUCinf), calculated as the sum of AUC0-last and the area extrapolated to infinity: AUCinf = AUC0-last + Clast/k where Clast would be the last guantifiable concentration. All NCA analyses will be conducted using Phoenix® WinNonlin® 6.4 (Pharsight, a Certara Company, CA).

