## 7.3 Final Analysis Plan

An objective of this study is to determine PK parameters ( $C_{max}$ , AUC and ratio of SC drug concentration during uptake and clearance) of diclofenac in healthy adults and TS data after using Flector® (diclofenac epolamine 1.3% patch) and Pennsaid® (2% diclofenac sodium topical solution) for the purpose of IVIVC by collecting data over two separate application periods.

Analysis of variance (ANOVA) followed by post-hoc Bonferroni test will be used for comparing the differences in the means of the PK parameters and significant differences will be declared at p<0.05. The statistical comparisons will be conducted as follow:

If diclofenac PK concentrations are found to be non-normally distributed, then we will examine Box-Cox transformations (e.g., log, square-root, etc.) that can achieve normality. If no transformation can achieve normality, then will use permutation tests to compute empirical *p*-values, and will use the bootstrap to compute standard errors and confidence intervals that account for within-person correlation.

IVIVC will be conducted comparing PK parameters and profiles to predicted PK parameters and profiles using IVPT and in vitro TS results. Multiple methods will be implemented to develop an IVIVC. The first method is to compare the steady state concentrations. The predicted steady state concentration using IVPT data will employ the following formula:

$$C_{ss} = \frac{J_{ss} * A}{CL}$$

The second method will compare the PK profiles of the clinical and IVPT study by predicting diclofenac concentrations at each time point in the IVPT study and comparing it to the clinical PK profile. The third method will be to determine and compare residual patch analysis between in vitro and in vivo.

In terms of developing an IVIVC for the TS study a comparison will be made between in vitro and in vivo uptake (absorption) and clearance diclofenac amounts. The second method is to compare the clearance to uptake diclofenac amount ratio between in vitro and in vivo.

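### Section 7.1 draws a product-level conclusion from Cmax and AUC, but the PK sessions compare regimens: 560 cm² of patch for 10 h against 400 cm² of solution for 6 h

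*Combined protocol and SAP*

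**What the plan says.** Section 7.1 begins from the position that the tested products are not bioequivalent. It then sets up a null hypothesis that the mean TS clearance/uptake ratio, Cmax and AUC "between these products are different (i.e., outside the 80–125% range". The units being compared are the products. Area, wear time and amount applied are not mentioned.

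Section 4 gives the PK regimens. In Study Session 1, four 140 cm² patches, "two patches/arm] will be applied for 10 h and removed". In Study Session 2, 4 g of solution over 400 cm² "will be applied to the skin for 6 h and removed". The design statement reads "This is designed as an open-label, non-placebo controlled, crossover study", but patch is described in Session 1 and solution in Session 2, and no allocation to sequence appears in the text supplied.

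Section 7.2 defines Cmax and two versions of AUC: AUC0-last, "determined by the linear trapezoidal method; and AUC value extrapolated to infinity". It divides neither by area, wear time nor dose. Section 7.1 does not say which AUC it means.

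Section 7.3 uses ANOVA with a Bonferroni post-hoc test for "comparing the differences in the means of the PK parameters and significant differences will be declared at p<0.05". It does not name the factor compared. It then says "The statistical comparisons will be conducted as follow", but the next paragraph deals with non-normal data and no list of comparisons follows. Area enters section 7.3 only through the formula Css = Jss × A / CL, which is used for the IVIVC prediction.

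**The concern.** Cmax and AUC after dermal application depend on how much skin is covered and for how long, as well as on the product. Here both differ, and both differ in the same direction. Session order is tied to product as well. A patch/solution ratio of raw Cmax or AUC is a sound estimate for the two regimens as applied, but it cannot separate the product from area, wear time and order.

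Section 7.1 nevertheless words the hypothesis for the products and presumes the answer. A ratio outside 80–125% could then be reported as bearing out non-bioequivalence of the products when the regimens alone could have produced it. A ratio inside the range could be reported as product similarity when it would in fact reflect lower delivery per unit area from the patch. What is at stake is the conclusion that may be drawn, not the validity of the data.

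**Working it through.** The plan gives no expected ratio, so there is no stated figure to reproduce. All ratios below are patch/solution.

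**Inputs (section 4, Study Sessions 1 and 2)**
- Patch: 4 × 140 = 560 cm², worn 10 h.
- Solution: 2 × 200 = 400 cm², worn 6 h.

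**Regimen ratios**
- Area: 560 / 400 = 1.40.
- Area × wear: (560 × 10) / (400 × 6) = 5600 / 2400 = 2.33.

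**Link to Cmax.** By the plan's own formula, Css = Jss × A / CL. With the same subjects and the same clearance, the ratio of plateau concentrations is the flux ratio per cm² × 1.40. For it to lie in 0.80–1.25, the flux ratio must lie between 0.80 / 1.40 = 0.57 and 1.25 / 1.40 = 0.89.

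**Link to AUC.** With linear kinetics, AUCinf equals amount absorbed divided by clearance. If the amount absorbed is proportional to area × time, the AUC ratio is the delivery ratio per cm²-hour × 2.33. For it to lie in 0.80–1.25, that delivery ratio must lie between 0.80 / 2.33 = 0.34 and 1.25 / 2.33 = 0.54.

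**How far this depends on proportionality.** The documents give no flux or half-life, so these are ranges under stated assumptions.
- If Cmax is reached at removal, before plateau, the factor 1.40 becomes 1.40 × (1 − 2^(−10/t)) / (1 − 2^(−6/t)) for half-life t. This gives 1.42, 1.55 and 1.78 at t = 1, 2 and 4 h, with a limit of 2.33.
- If a skin reservoir continues to release drug for a mean of m h after removal, the AUCinf factor becomes 1.40 × (10 + m) / (6 + m). This gives 2.33 at m = 0 and 1.87 at m = 6, with a limit of 1.40.

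In these cases the regimen factor stays between 1.40 and 2.33.

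**Does scaling remove the problem?** Not reliably. Suppose flux per cm² is truly equal:
- Cmax per cm² is the Cmax factor above divided by 1.40. It rises from 1.00 at plateau towards 10 / 6 = 1.67 at long half-lives.
- AUCinf per cm²-hour is (1 + m/10) / (1 + m/6). At m = 6 this is 1.6 / 2.0 = 0.80.
- If solution input stops at 3 h, AUCinf per cm²-hour is 6 / 3 = 2.00.

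**TS sites (section 4, Study Session 3).** Every site is 8.25 cm² for both products, so the area ratio is 1.00. Wear is still 10 h against 6 h, a ratio of 1.67.

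**The case against.** The regimens are stated openly in the summary and in section 4, and an attentive reader would see that the ratio is one of regimens. The first study objective is "Generate human PK data for the purpose of establishing an IVIVC model", and the second does the same for TS. For that purpose the measured concentrations are what should be compared with prediction. No passage supplied ties a decision to the between-product ratio, and no estimate or sample would change. This stands, and it is why the impact is limited. It does not remove the point: section 7.1 is the only stated hypothesis, and its wording attributes the result to the products.

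It is also fair that the comparisons announced in 7.3 may have been listed in text that is not available, and that 7.3 names no ANOVA factor. The claim that no rule exists is therefore less certain for 7.3 than for 7.1.

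Three stronger readings are tempting, and the documents do not support them:
- *The raw ratios will fall outside 80–125%.* That would need roughly equal flux per cm². No passage supports this, and the salts, vehicles and labelled loads differ: 4 × 180 / 560 = 1.29 mg/cm² against 4 × 20 / 400 = 0.20 mg/cm².
- *Normalised Cmax and AUC would recover a product comparison.* The working shows that they can mislead in either direction. TS clearance sampling 17 h and 41 h after removal implies that retained skin drug is expected. The residual-drug analysis covers patches only, so it gives no common scale.
- *The areas, wear times or session order have spoiled the study.* The regimens serve the IVIVC. There is at least a one-week washout between sessions, and no order effect is quantified.

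**Conclusion.** The point holds at the level of interpretation. Raw Cmax and AUC compare 560 cm² for 10 h with 400 cm² for 6 h, in a fixed session order in the text supplied. A ratio on either side of the 80–125% limits cannot be assigned to the products. The documents' own figures give regimen factors of 1.40 (area) and 2.33 (area × wear). The bands of 0.57–0.89 and 0.34–0.54 additionally assume linear kinetics and proportionality, with a plateau for Cmax and no depletion or reservoir for AUC. They show what a result inside the range would mean; they do not predict this trial's result.

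The TS ratio is less affected because site areas are equal, but it is not exempt, since wear time differs there too.

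Confidence is high for 7.1 and moderate for 7.3. The impact is limited by the IVIVC aim, but the correction is worth making because it settles what the trial may conclude.

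**What to change.** In section 7.1, replace both the opening premise and the product-level wording. Adding a disclaimer beside the premise would leave the section asserting and denying the same thing. Suggested text:

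*The 80–125% comparison of Cmax and AUC [state AUC0-last, AUCinf or both] concerns the regimens as applied (560 cm² of patch for 10 h and 400 cm² of solution for 6 h, in the session order given). It will not be read as evidence of product bioequivalence or non-bioequivalence. The TS clearance/uptake ratio likewise compares 10 h with 6 h of wear, at equal site area.*

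In section 7.3, repeat the limit for the ANOVA and supply or restore the announced list of comparisons. If that list already contains such a limit, a cross-reference from 7.1 is enough.

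Optionally, report Cmax per cm² and AUC per cm²-hour as descriptive summaries. State their assumptions (plateau for Cmax; near-constant flux without depletion or reservoir for AUC) and do not test them against 80–125%. Keep raw PK for the IVIVC.

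The cost is a few sentences, plus division by known constants if the optional summaries are used. No new samples are needed and the applied regimens need not change. The downside is a narrower between-product conclusion; session order also remains tied to product whatever scaling is reported.
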